 To evaluate the levels of ocrelizumab in the mother during pregnancy 	 Serum concentration of ocrelizumab in the mother during pregnancy (time frame of blood sampling: Week 24–30, Week 35) and at delivery (time frame of blood sampling: within 24 hours after delivery) 	
Safety Objectives		
• To evaluate the safety of ocrelizumab in the mother, and the safety of infants potentially exposed to ocrelizumab	 Rate and nature of adverse events in the mother throughout the study, including changes in clinical and laboratory results 	
	 Rate and nature of adverse events in the infant throughout the study, including infections and hospitalizations 	
To evaluate pregnancy and neonatal outcomes	 Proportion of pregnancies resulting in live births (term and preterm, with and without congenital anomalies), therapeutic abortions, or stillbirths 	
	Infant characteristics at birth, including but not limited to body weight, head circumference and length	

ASQ-3 = Ages and Stages Questionnaire, version 3; EDSS = Expanded Disability Status Scale; HBV = hepatitis B virus; Hib = Hemophilus influenzae type b; LLN = lower limit of normal; MMR = measles, mumps, and rubella; MS = multiple sclerosis; PCV-13 = 13-pneumococcal conjugate vaccine; SARS-CoV-2 = severe acute respiratory syndrome coronavirus 2; sNfl = serum neurofilament light chain; WHO = World Health Organization.

[
Objectives	Corresponding Endpoints
Exploratory Objectives	
 To evaluate the infant's growth velocity and developmental milestones in the first year of life 	 Assessment of growth velocity based on age-adjusted body length, weight and head circumference, using growth charts according to the WHO Child Growth Standards, as well as absolute values, at Months 2, 4, 6, 9, and 12
	 Assessment of child developmental milestones in the domains of communication, gross motor, fine motor, problem solving, and personal-social at Months 2, 4, 6, 9, and 12, using the ASQ-3
 To evaluate humoral immunity to clinically relevant pathogens in mothers during pregnancy 	 Mean titers of antibody immune response(s) to vaccinations, measured in the third trimester (time frame of blood sampling: Week 35.
	 Percentage of women with positive humoral response (seroprotective titers; as defined for the individual vaccine) to vaccines (time frame of blood sampling: Week 35.

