6. STATISTICAL CONSIDERATIONS AND ANALYSIS PLAN

The analysis of this open-label study will be primarily based on descriptive statistical methods. Unless otherwise specified, no statistical tests are planned. Corresponding 95%CIs will be presented as appropriate.

The primary analysis will be performed after the last blood draw at Week 6 to examine B-cell levels in infants. The full analysis, including the analysis of growth velocity of the infants in the first year, will be conducted at the end of the study.

Full details of all statistical aspects and planned statistical analyses will be specified in a separate statistical analysis plan (SAP), which will be finalized prior to the locking of the study database and may include further exploratory analyses not explicitly described in this section.

Analysis Populations

Full analysis set (FAS)

Two separate FAS populations will be considered:

- Women's FAS: this will include all pregnant women defined through the inclusion and exclusion criteria in the study who were exposed to ocrelizumab either 0–6 months before the last menstrual period or in the first trimester of pregnancy (i.e., up to gestational Week 13 [inclusive]).
- Infants' FAS: includes all infants born to women in the FAS who were potentially exposed to ocrelizumab during pregnancy.

Safety Population

The safety population for the women is the same as the FAS. The safety population for infants will include all infants of mothers in the FAS population.

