4. STATISTICAL METHODS

The analysis of this open-label study will be primarily based on descriptive statistical methods. Unless otherwise specified, no statistical tests are planned. Corresponding 95% Cls will be presented as appropriate.

For continuous variables, descriptive statistics (e.g., number of patients [n], mean, standard deviation [SD], median, 25th and 75th percentiles, minimum, maximum) will be calculated and summarized.

For categorical variables, the number and percentage in each category will be displayed.

The analyses outlined in this Statistical Analysis Plan (SAP) supersede those specified in the protocol.

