4.6.1 Infants Growth Velocity

Infant growth velocity will be assessed by recording the infant's weight (kg), height (cm) and head circumference (cm) at birth, and Months 2, 4, 6, 9 and 12. The visit label will be derived based on infants actual age at the time of assessment: Month 2 (31-91 days), Month 4 (92-152 days), Month 6 (153-227 days), Month 9 (228-318 days), Month 12 (319-409 days), Month 13 (\geq 410 days).

Analysis will be based on the SAFI and includes:

- Actual values and change from baseline (defined as at birth) for weight, length/height, head circumference, and growth velocity (defined as the change from baseline divided by the number of months since baseline) will be summarized at each age time-point (birth, Months 2, 4, 6, 9, and 12).
- The weight-for-age and length/height-for-age percentiles and change from baseline percentiles at each time-point will be summarized.
- The number and percentage of infants in the 3rd, 5th, 10th, 25th, 50th, and >50th percentile of the WHO growth charts will be presented for weight-forage and length/height-for-age percentile at each time point. The number and percentage of infants within 10th-90th percentile, and 3rd-97th percentile of the WHO growth charts will also be presented.

- Shift tables will be presented for each parameter to compare the change from infant's percentile at baseline (≤3rd, >3rd ≤5th, >5th ≤10th, >10th ≤25th, >25th -≤50th, >50th) to each time-point (WHO 2006; WHO 2007; WHO 2017).
- Mean percentiles for weight-for age and length/height-for-age and corresponding 90% CIs will be plotted over time.
- Individual growth charts will be presented for each infant. This chart will
 present the weight and length/height for the infant over time, including
 reference lines for the 3rd, 25th, 50th, 75th, 90th and 97th percentiles for
 weight-for-age and length/height-for-age from WHO growth charts. Separate
 plots will be produces for each infant. Combined plots will also be produced for
 males and females separately, to show the trajectories of each infant on the
 same page.

All observed assessments will be included in the analysis; no imputation for missing assessments will be performed. The analysis will be based on the SAFI. Analysis will also be presented for the following subgroups:

- Type of feed: exclusive breast milk from birth to Month 6 vs others (including complementary feeding [breastmilk + formula milk, in various proportions] and formula feeding [no breast milk]).

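### SAP 4.6.1 does not name head circumference in four of its five WHO-percentile outputs, reports velocity only as an average since birth, and plots mean percentiles with unexplained 90% CIs

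*SAP*

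**What the plan says.** Protocol Section 2 (Table 1, exploratory objectives) gives the endpoint as "Assessment of growth velocity based on age-adjusted body length, weight and head circumference, using growth charts according to the WHO Child Growth Standards", with absolute values as well. Protocol 6.4.3 leaves the derivations of exploratory endpoints to the SAP, and SAP Section 4 states that its analyses replace those in the protocol.

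SAP 4.6.1 collects weight, height and "head circumference (cm) at birth, and Months 2, 4, 6, 9 and 12". It then plans:

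- actual values, change from birth, and "growth velocity (defined as the change from baseline divided by the number of months since baseline", for weight, length/height and head circumference;
- a percentile summary by visit: "The weight-for-age and length/height-for-age percentiles and change from baseline percentiles at each time-point will be summarized";
- counts in WHO percentile categories, for weight-for-age and length/height-for-age;
- shift tables from birth to each visit: "Shift tables will be presented for each parameter", citing WHO 2006, 2007 and 2017;
- a plot: "Mean percentiles for weight-for age and length/height-for-age and corresponding 90% CIs will be plotted over time";
- individual charts with WHO reference lines, and combined plots by sex, for weight and length/height;
- a listing of all growth data.

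On interval level, SAP Section 4 gives the general rule: "no statistical tests are planned. Corresponding 95" per cent intervals are the default. Protocol Section 6 has the same rule and says that they "will be presented as appropriate".

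**The concern.** Three features of 4.6.1 fit the endpoint poorly.

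First, head circumference on WHO charts is part of the endpoint, but most of the outputs that use WHO percentiles do not name it. Because the SAP takes precedence, a programmer who follows it literally would produce little WHO-standardised head-circumference analysis.

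Second, the only velocity statistic is the average since birth. At later visits it is dominated by early growth, so a change in the last interval is diluted.

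Third, the group plot averages percentiles, which are bounded and non-linear, and shows 90% intervals where the stated convention is 95%.

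What is at stake is how clearly growth can be described in about 30 potentially exposed infants. No test or decision rule depends on it.

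**Working it through.** The plan gives no figure for this analysis, so there is none to reproduce. The inputs are the nominal visits (birth and Months 2, 4, 6, 9, 12) and the definitions in SAP 4.6.1, and the 30 evaluable infants expected in SAP 2.2.

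**1. Coverage of head circumference**

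| WHO-percentile output in SAP 4.6.1 | Parameters named |
|---|---|
| Percentile summary by visit | weight, length/height |
| Percentile-category counts | weight, length/height |
| Mean-percentile plot | weight, length/height |
| Individual and combined charts | weight, length/height |
| Shift tables | each parameter |

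Four of the five do not name head circumference. The 2007 entry in the SAP reference list is the WHO head-circumference-for-age standard, which suggests that the shift tables were meant to include it. The citation is not firm evidence, since the 2017 entry cited alongside it is a pertussis module.

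**2. Weight of the latest interval in the velocity**

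Velocity since birth at month b is the time-weighted mean of the interval velocities, so the last interval (a to b) has weight (b − a)/b:

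- Month 2: 2/2 = 100%
- Month 4: 2/4 = 50%
- Month 6: 2/6 = 33%
- Month 9: 3/9 = 33%
- Month 12: 3/12 = 25%

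Let r be normal Month 9–12 velocity divided by the first-year mean, and f the fractional fall in that interval. The Month 12 velocity then falls by f × r × 3/12. The documents do not give r; I assume 0.3 to 1.0.

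| Fall in Months 9–12 (f) | Fall in SAP velocity, r = 0.3 | Fall in SAP velocity, r = 1.0 |
|---|---|---|
| 25% | 1.9% | 6.3% |
| 50% | 3.8% | 12.5% |
| 100% | 7.5% | 25% |

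A between-visit velocity would show f in full.

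**3. Averaging percentiles**

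On the normal scale, a one-SD fall takes an infant from the 50th to the 15.9th percentile, a change of 34.1 points. The same fall from the 3rd percentile (z = −1.88) ends at the 0.2nd, a change of 2.8 points. The mean percentile therefore responds least for infants who are already small.

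A two-infant illustration: the 1st and 50th percentiles average (1 + 50)/2 = 25.5. The mean z is (−2.326 + 0)/2 = −1.163, which is the 12th percentile.

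**4. Interval level**

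With n = 30 (29 df) the t multipliers are 1.699 for 90% and 2.045 for 95%. The ratio is 1.699/2.045 = 0.83, so the 90% interval is 17% narrower; the 95% interval is 2.045/1.699 = 1.20 times as wide. If percentiles were uniform from 0 to 100 (SD = 100/√12 = 28.9, an assumption), the half-widths would be 9.0 and 10.8 percentile points.

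**The case against.** A reader might infer that the plan would miss a late slow-down altogether. For weight and length the documents do not support that. The SAP also plans change in percentile at each visit, a WHO chart for every infant, combined trajectories and full listings; with about 30 infants, one who stopped growing at Month 9 would be seen crossing reference lines. The shift tables add less, because they compare only with birth and pool everything above the 50th percentile: a fall from the 97th to the 51st shows as no shift. For head circumference the protection is thinner, since no individual chart and no percentile summary by visit is named.

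A reader might also infer that WHO head-circumference percentiles are left out, or that part of the endpoint goes unanalysed. Neither is established. The shift tables can fairly be read as including head circumference, and its actual values, change from birth and velocity are all summarised.

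It can further be said that the since-birth definition suits an objective framed over the first year of life, and that the documents do not name late faltering as the target. That is fair, and it is why between-visit velocity is only an optional addition. Between-visit velocity also has a weakness of its own. The SAP windows are contiguous (Month 9 ends at day 318 and Month 12 starts at day 319), so consecutive visits could be one day apart. Some protocol windows in Appendix 6 also touch, such as Months 2 and 4.

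Finally, SAP Section 4 supplies medians, quartiles and ranges by default, category counts do not depend on averaging, and the 95% convention applies only as appropriate. So neither the averaging nor the 90% level distorts the whole analysis. The level still has no stated reason.

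**Conclusion.** The point holds as a clarification and a cheap improvement.

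- Head circumference is not named in four of five WHO-percentile outputs, and is only plausibly covered in the fifth. This is the firmest part, because the protocol endpoint includes it.
- The velocity summary gives the Month 9–12 interval about 25% of the weight at Month 12. A complete stop then lowers that figure by 7.5% to 25%. The weight follows from the nominal visit months, and actual dates will move it somewhat; the range rests on the assumed ratio of 0.3 to 1.0. The slow-down is diluted in this one statistic, not hidden from the analysis of weight and length.
- The mean plot compresses change among small infants and uses intervals 17% narrower than the convention would give with 30 infants. The size of the averaging distortion in this cohort cannot be judged from the documents; the two-infant example is only an illustration.

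The endpoint is exploratory and descriptive, so no error rate, sample size or primary conclusion is affected.

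**What to change.** In SAP 4.6.1:

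1. Name head-circumference-for-age in every WHO-based output: the percentile summary, category counts, shift tables, and individual and combined charts.
2. Summarise and plot mean WHO z-scores by visit, with 95% CIs, for weight, length and head circumference, in place of the mean-percentile plot. Keep the percentile categories. If 90% is preferred, state why.
3. Optionally, show between-visit velocity beside the since-birth figure. Calculate it from actual measurement dates, with a pre-set minimum gap between measurements and a rule for a missed previous visit, since missing assessments are not imputed.

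The cost is SAP wording and a little more programming; head circumference is already collected. The CIs on one plot become wider (1.20 times at 30 infants for the same statistic), and between-visit velocities will be noisier than the since-birth figure, which is the reason to show both.

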- Maternal OCR exposure prior to the study in 3-month interval of before/during pregnancy (3-6 prior LMP, 0-3 month prior to LMP, 1st trimester)

All infant growth velocity data will be listed.

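### The growth shift tables and category list have one open class above the 50th WHO percentile, so movement within the upper half is not counted as a shift

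*SAP*

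**What the plan says.** Growth is an exploratory endpoint. Protocol Section 2 (Table 1) defines it as "Assessment of growth velocity based on age-adjusted body length, weight and head circumference", read against the WHO growth charts and as absolute values at Months 2, 4, 6, 9 and 12.

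SAP 4.6.1 specifies these percentile-based outputs:

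- A summary of percentiles: "The weight-for-age and length/height-for-age percentiles and change from baseline percentiles at each time-point will be summarized".
- A category table: "The number and percentage of infants in the 3rd, 5th, 10th, 25th, 50th, and >50th percentile of the WHO growth charts", for weight-for-age and length/height-for-age. The same bullet adds two bands: "The number and percentage of infants within 10th-90th percentile, and 3rd-97th percentile of the WHO growth charts will also be presented".
- Shift tables: "Shift tables will be presented for each parameter to compare the change from infant's percentile at baseline" to each later time point, with classes "≤3rd, >3rd ≤5th, >5th ≤10th, >10th ≤25th, >25th -≤50th, >50th".
- A plot of mean percentiles over time for weight and length/height.
- Charts: "Individual growth charts will be presented for each infant", showing weight and length/height with reference lines at the 3rd, 25th, 50th, 75th, 90th and 97th. Combined plots by sex are also planned.
- A listing: "All infant growth velocity data will be listed".

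The percentile summary, the category counts, the mean plot and the charts name weight and length/height only. The shift tables are for each parameter. Their bullet cites the 2007 WHO reference, which the SAP reference list identifies as the head-circumference standard.

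**The concern.** A shift table shows who has moved between baseline and follow-up, and on a growth endpoint the interest is in infants who cross percentile lines, downward above all. Here the lower half of the reference is cut into five classes and the upper half into none. An infant who starts above the median can lose a good deal of relative size and remain on the diagonal, as can one who rises.

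The two extra bands do not close the gap. They are marginal counts at each time point and do not link an infant's baseline to the later value. A fall from the 89th to the 51st lies inside both bands at both times. A fall from the 97th to the 51st shows only as an entry into the 10th-90th band, which reads as normalisation.

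What is at stake is the count of infants whose growth slows from an above-median start. No primary or secondary result depends on it.

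**Working it through.** The plan states no figure for the share of infants above the 50th or for missed shifts, so there is none of its own to reproduce.

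**Inputs from the documents.** Class boundaries at the 3rd, 5th, 10th, 25th and 50th (SAP 4.6.1); about 30 evaluable infants (SAP 2.2).

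**Inputs assumed.** z-scores at birth and later are standard normal on the WHO reference, jointly normal, with correlation r = 0.3, 0.5 or 0.7. Neither document gives r.

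**Step 1: what one cell can hide.** The size of a move is the difference in normal quantiles.
- 89th to 51st: 1.227 - 0.025 = 1.20 SD, no shift.
- 97th to 51st: 1.881 - 0.025 = 1.86 SD, no shift.
- 51st to 49th: 0.025 + 0.025 = 0.05 SD, counted as a shift.

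For comparison, the closed classes are 0.24 (3rd-5th), 0.36 (5th-10th), 0.61 (10th-25th) and 0.67 SD (25th-50th) wide.

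**Step 2: how many infants share the open class.** Expected counts are 30 × (0.03, 0.02, 0.05, 0.15, 0.25, 0.50) = 0.9 / 0.6 / 1.5 / 4.5 / 7.5 / 15. If the cohort's mean z is m with SD 1, the share above the 50th is Φ(m): 31% at m = -0.5, 50% at 0 and 69% at +0.5, or 9.3, 15 and 20.7 of 30.

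**Step 3: how many falls are missed.** The change in z has SD √(2 - 2r), so P(fall ≥ t) = Φ(-t / √(2 - 2r)). The share of those falls that stays in the same class comes from simulating at least 10^6 bivariate normal pairs for each r. Missed infants = 30 × P(fall) × share.

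| Fall | r | P(fall) | Falls in 30 | Share in same class | Missed per time point |
|---|---|---|---|---|---|
| ≥ 0.67 SD | 0.3 | 0.286 | 8.57 | 0.207 | 1.77 |
| ≥ 0.67 SD | 0.5 | 0.251 | 7.54 | 0.243 | 1.83 |
| ≥ 0.67 SD | 0.7 | 0.194 | 5.80 | 0.285 | 1.65 |
| ≥ 1 SD | 0.3 | 0.199 | 5.97 | 0.165 | 0.99 |
| ≥ 1 SD | 0.5 | 0.159 | 4.76 | 0.198 | 0.94 |
| ≥ 1 SD | 0.7 | 0.098 | 2.95 | 0.236 | 0.70 |

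At least 98% of the missed falls lie in the open upper class, so the missing cuts above the 50th cause nearly all of the loss. For falls of 1.86 SD or more, the expected number missed is only 0.03 to about 0.13.

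**Step 4: effect of added cuts.** With boundaries at the 75th, 90th and 97th as well, the same-class share drops to between 0.001 and 0.010. The expected 15 infants above the 50th become 30 × (0.25, 0.15, 0.07, 0.03) = 7.5 / 4.5 / 2.1 / 0.9.

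**The case against.** The strongest reply is that the falls are shown elsewhere. For weight and length, change from baseline in percentile is summarised at every time point, and SAP Section 4 gives median, quartiles, minimum and maximum as the example statistics for continuous variables. An 89th-to-51st fall enters as 51 - 89 = -38 points, and the minimum or lower quartile would expose it. The charts carry lines at the 75th, 90th and 97th, all data are listed, and growth velocity itself is summarised for all three measures. With about 30 infants, a reader can find every fall in the listing.

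This stands. A reader might infer from the open class that a large fall registers nowhere, or that only averages and charts read by eye remain; the documents do not support either. A reader might also assume that about half the cohort sits above the 50th. No document says so, and the assumption fails if the cohort's mean departs from the WHO reference. Nor does every upper-half fall go unseen: a 75th-to-50th fall does register, because the 50th belongs to the class below.

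It can also be said that finer classes at the low end suit a table aimed at small infants, and that a 9 × 9 grid for 30 infants would be mostly zeros and ones. The first is a coherent choice, but it does not need the upper half to be uncut. The second is a real cost, though the existing lower classes already expect 0.9, 0.6 and 1.5 infants.

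Two things survive. Distribution summaries, charts and listings do not yield a count of infants who moved. And they do not extend to head-circumference percentiles, for which only absolute values, their change and velocity are otherwise summarised.

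**Conclusion.** The point holds as a limited presentational gap. The shift tables and main category list do not subdivide above the 50th, so movement there is not counted by any planned table. For weight and length it can still be seen in other outputs. For head circumference the shift table is the only percentile-based output specified, provided the tables for each parameter include it; the citation of the head-circumference standard suggests this, but the SAP does not say so outright.

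The size is about 0.7 to 1.0 infants of 30 per time point for falls of at least 1 SD, and about 1.65 to 1.83 for falls of at least 0.67 SD. This rests on a WHO-like cohort, joint normality and an assumed correlation of 0.3 to 0.7. The share of infants in the open class is likewise an assumption, about 31% to 69% for a mean z between -0.5 and +0.5. The endpoint is exploratory and no tests are planned, so this is a worthwhile improvement and not a threat to any conclusion.

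**What to change.** In SAP 4.6.1, replace the class above the 50th with four: >50th to ≤75th, >75th to ≤90th, >90th to ≤97th, and >97th. Do this at least in the overall shift tables and the category list; the feeding and exposure subgroup tables could keep the six classes. It would help to state in the same bullet whether head circumference is among the parameters shifted.

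The cost is a few words in the SAP and three more rows and columns per shift table, from 6 × 6 = 36 to 9 × 9 = 81 cells, with sparser cells as a result. No new data are needed, and all three cuts are already drawn on the individual charts. The change is cheapest before the tables are programmed.
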